2.2 Questionnaire

At the third time point patients will be contacted by phone, after receiving written informed consent by mail. The study and its rationality will be introduced together with the main objectives. The input needed from the patients will be communicated and an oral informed consent will be requested. In case of a positive input the following questions will be asked:

- How much pain do you experience at the moment in the knee where the procedure was performed in a scale of zero to ten where zero is 'no pain' and ten is 'unbearable pain'?
- Is the pain in the knee tolerable or not?
- How much effect do you still perceive at the moment expressed in percent between 0 and 100%?
- How long do you think the treatment worked or is there still effect?
- Do you experience at the moment functional improvement in comparison with before the treatment?
- Which pain medication are you using at the moment?
- Did you experience any adverse events?

The conversation will be executed in the Dutch language.

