The first described conventional radiofrequency ablation of the genicular nerves is presented by Choi and colleagues in 2011. (10) In this double blind randomized trial patients showed significant improvement in pain and functionality scores in comparison with placebo. Since this first positive report, multiple investigations have explored and expanded the use of radiofrequency ablation towards pulsed radiofrequency and cooled radiofrequency treatment as alternatives to the conventional ablation. (11-13)

In the present retrospective cohort study we will analyze patients treated with this novel technique in our chronic pain center. The main aim of this study is to determine treatment success of radiofrequency ablation on patients with chronic knee pain. Furthermore, we aim to gain a better insight in demographics, indications, referring physicians, complications and adverse events that might be beneficial for organizing care for chronic knee pain patients.

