4. STUDY OBJECTIVES

4.1 **The primary objective** of this study is to evaluate the treatment success of the conventional radiofrequency treatment of the genicular nerves in patients on patients diagnosed with chronic knee pain due to osteoarthritis of the knee or PPSP at six weeks post treatment. Treatment success is defined as a global perceived effect of at least 50% at measurement time point compared to baseline.

4.2 **The secondary objectives** are:

- Evaluation of treatment effect at a third time point at the end of the inclusion period
- Subgroup analysis of treatment success based on indication to treatment
- Evaluation of subjective functional improvement
- Evaluation of change in analgesics
- Estimation of the duration of effect of the treatment
- Adverse event

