8. INFORMED CONSENT

Patients in accordance with eligibility criteria will be contacted by mail to obtain written informed consent and afterwards by phone by the investigator. At the beginning of the contact oral informed consent will also be obtained.

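### The phone script presents the study's rationale and objectives just before the subjective third-time-point ratings, and nothing separates the caller from the treating physician or the week-6 scores: an avoidable bias risk in secondary endpoints

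*Combined protocol and SAP*

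**What the plan says.** Section 2.2 (Questionnaire) sets the order of the call. First, "The study and its rationality will be introduced together with the main objectives". Next, "The input needed from the patients will be communicated and an oral informed consent will be requested". Then, "In case of a positive input the following questions will be asked", and the list covers current pain on a zero-to-ten scale, tolerability, percent effect, how long the treatment worked, functional improvement, medication and adverse events. The percent-effect item reads "How much effect do you still perceive at the moment expressed in percent between 0 and 100" percent.

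Section 8 (Informed consent) says that patients are "contacted by mail to obtain written informed consent and afterwards by phone by the investigator". Sections 2.1 and 2.2 confirm that written consent comes before the call.

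On the aim of the study, section 1 states: "The main aim of this study is to determine treatment success of radiofrequency ablation on patients with chronic knee pain". Section 4.1 adds: "Treatment success is defined as a global perceived effect of at least 50% at measurement time point compared to baseline".

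The schedule in section 6 records the treating physician as a variable. No section uses it to decide who may call whom, and none says which earlier scores the caller may see. Blinding is mentioned only where cited trials are described or listed.

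**The concern.** The patient is told why the study is done and what it sets out to show, and a moment later is asked by the investigator how well the treatment worked. Three sources of bias are open. The patient may answer in line with the stated purpose (expectation). The patient may wish to please the team that gave the treatment (courtesy). A caller who knows the week-6 score may settle a vague answer towards it (interviewer bias).

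Every patient in this cohort was treated and no comparator is described, so a shift of this kind does not cancel in a between-group contrast. All patients hear the same introduction, so no analysis can estimate its effect afterwards. The third-time-point GPE success rate, NRS reduction, functioning and duration of effect are at stake. They carry what the protocol has to say about the later effect of the treatment.

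**Working it through.** The documents give no sample size, variance or effect size for these endpoints, so there is no figure of the plan's own to reproduce. The check is a comparison of sections.

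**1. Order of events.** Section 2.2 places introduction, consent request and ratings in one call, in that order. Nothing comes between the objectives and the ratings except the consent step.

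**2. Who calls.** Section 8 names the investigator. Sections 2.1, 2.2, 6 and 8 contain no requirement that the caller be independent of treatment or unaware of week-6 values. The protocol does not say that the treating physician will call; it leaves this open.

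**3. Which endpoints depend on the call.**

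| Endpoint (section 5) | Source | Exposed to the script? |
|---|---|---|
| GPE success at week 6 (primary) | patient file, consultation (2.1, 6) | No |
| NRS at week 6 | patient file, consultation (2.1, 6) | No |
| GPE success, third time point | phone call (2.1, 2.2) | Yes |
| NRS, third time point | phone call (2.1, 2.2) | Yes |
| Subjective functioning | phone call only, according to the schedule (6) | Yes |
| Duration of effect | asked only in the phone script (2.2) | Yes |

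**4. Question wording.** The percent-effect item contains the word *still*, and its scale runs from 0 to 100%, so worsening cannot be recorded. The functioning item asks about improvement only. The duration item takes it that the treatment worked for some time. The NRS item is neutral.

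**5. Route into the model.** Section 7 regresses post-treatment pain on time since treatment to obtain 3- and 6-month estimates. The schedule has post-treatment NRS only at the week-6 consultation and by phone. Mode of collection therefore moves with time, and a shift in the phone scores enters those estimates.

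**6. Direction of the comparison between time points.** Let b_c be the bias in the week-6 clinic rating and b_p the bias in the phone rating. The week-6-to-phone comparison is distorted by b_p − b_c. The script bears on b_p only. The documents give neither term, so the sign of the difference is unknown.

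**7. Illustration of size (all inputs are assumptions).** Let p be the share of patients whose unbiased rating lies just under the threshold (40–49%), and q the share of those whose answer is lifted to 50% or more. With no movement the other way, the rise in the success proportion is p × q:

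- p = 0.10, q = 0.25: 0.10 × 0.25 = 0.025, or 2.5 percentage points
- p = 0.20, q = 0.50: 0.20 × 0.50 = 0.10, or 10 percentage points
- q = 0: no change

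A downward shift of d points in the phone NRS adds d to the reported reduction, because the baseline value is already on file. An assumed d of 0.3 to 0.5 adds 0.3 to 0.5 points. These figures show how the endpoints respond to a shift; they are not evidence that one occurs.

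**The case against.** The introduction leads into a request for oral consent, and explaining a study before asking for consent is ordinary practice. The mailed text is not among the documents reviewed, so one cannot be sure that it covers everything the call would then omit. Patients will have read about the study anyway, and the questions themselves reveal its purpose. The change removes a repetition, not the knowledge. This stands, and it limits the gain. It does not remove the case for avoiding that repetition directly before the ratings, or for keeping the caller apart from the treatment and the earlier scores.

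A reader might infer that patients are told the 50% threshold, or told that the technique is promising. The documents do not support this. Those statements are in parts of the protocol written for its readers, and the spoken introduction is not reproduced. The illustration of size therefore cannot be read as the effect of announcing a cut-point.

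A reader might also infer that the bias is peculiar to the third time point and makes the effect look more lasting than it is. That does not follow. The week-6 ratings come from a consultation at the clinic that gave the treatment (section 3.1) and may carry courtesy bias of their own, as large or larger.

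Finally, lack of treatment masking is not a fault that could be mended here, since all patients know they were treated. Only the caller's independence and knowledge of earlier scores can be controlled.

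**Conclusion.** The point holds as an avoidable risk of expectation, courtesy and interviewer bias in the secondary third-time-point endpoints. It rests on the order of the call in section 2.2, the caller named in section 8, and the absence of any rule separating that caller from treatment or from the week-6 values. The primary endpoint is untouched.

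The documents do not show that bias occurred, how large it would be, or whether it would exceed any bias in the clinic ratings. The 2.5 to 10 percentage points and the 0.3 to 0.5 NRS points are assumption throughout, and zero is also possible. The reason to act is that the remedy is cheap and that no later analysis can undo the effect. It is a modest improvement to the plan and does not put the main result in doubt.

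**What to change.** Rewrite section 2.2 and align section 8 with it:

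- Keep the full study information, including rationale and objectives, in the mailed consent material, and confirm that it is complete there.
- Open the call with a short, fixed, neutral statement (for example, that the team would like to ask how the knee is now) and an oral confirmation of consent.
- Ask the outcome questions in fixed order and as worded. Make the wording neutral: drop *still*, and let the patient report no change or worsening for effect and for function.
- Answer questions about the study after the ratings.
- Where the existing team allows, have the call made by a member who did not treat that patient, on a form that does not show the week-6 GPE or NRS.
- Record who made each call and whether that person treated the patient, so that exceptions can be reported.

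The cost is the rewording, some allocation of calls by treating physician, and preparation of the form. The documents do not give the size of the team, so the non-treating caller is conditional on it. No visit is added. Some awareness of the purpose will remain, and the difference between clinic and telephone collection in the section 7 model is not removed by this change and should be stated as a limitation.

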2. STUDY DESIGN

2.1 Study design

This study is designed as a retrospective longitudinal cohort study of patients treated with a radiofrequency treatment of the genicular nerves in a single-center (ZOL, Genk) between 1 September 2017 and 30 June 2020. Each knee will be considered as a unique observation, and bilateral procedures were assessed specific to each knee treated. Data retrieved from the patient files will be collected at baseline, 6 weeks post-intervention and telephonically at a third time point which ranges from 6 weeks to 3 years after the procedure. The following demographic and clinical data will be collected at baseline: patient age, sex, NRS score, length of symptom duration, indication for the procedure, use of strong opioids, history of previous knee surgery and the referring physician. Strong opioid analgesics are defined as all opioids excluding tramadol and codeine.

Data collected at 6 weeks post-intervention will include: NRS, GPE, adverse events, and concomitant use of strong opioids.

Patient's data will be collected at a third time point. Written informed consent will be obtained by mail prior to contact by phone. After receiving informed consent, patients will be contacted by telephone and data will be gathered on the same variables as at 6 weeks post-intervention and on subjective functional outcome.

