5. STUDY ENDPOINTS

5.1 Primary endpoint:

Proportion of patient with treatment success at week 6 defined as a global perceived effect of $\geq 50\%$ compared to baseline.

5.2 Secondary endpoints:

- Proportion of patients with treatment success at third time point defined as a global perceived effect of $\geq 50\%$ compared to baseline.
- NRS reduction at week 6 and at the third time point.
- Subjective physical functioning at week 6 and at the third time point.
- Duration effect of the treatment defined as the period with a GPE of $\geq 50\%$.
- Change in use of strong opioids at week 6 and at the third time point.
- Safety: number/type of adverse events.

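### The telephone question that supplies GPE at the third time point is not anchored to baseline, although success there is defined against baseline

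*Combined protocol and SAP*

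**What the plan says.** Section 4.1 sets one rule for every time point: "Treatment success is defined as a global perceived effect of at least 50% at measurement time point compared to baseline". Section 5.2 repeats it as a secondary endpoint: "Proportion of patients with treatment success at third time point defined as a global perceived effect of" 50% or more, again against baseline.

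The telephone script in section 2.2 contains one item that can yield this percentage: "How much effect do you still perceive at the moment expressed in percent between 0 and 100"%. In the same list, the function item reads "Do you experience at the moment functional improvement in comparison with before the treatment".

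For week 6, section 2.1 only names the variable: "Data collected at 6 weeks post-intervention will include: NRS, GPE, adverse events, and concomitant use of strong opioids". No question text, anchors or scale are given there or in the section 6 schedule. Section 2.1 states that by telephone "data will be gathered on the same variables as at 6 weeks post-intervention and on subjective functional outcome". The sources differ: "Data retrieved from the patient files will be collected at baseline, 6 weeks post-intervention and telephonically at a third time point". The call comes at "a third time point which ranges from 6 weeks to 3 years after the procedure".

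Section 7 does not mention GPE, and no section says how the telephone answer becomes a GPE relative to baseline.

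**The concern.** The endpoint needs the present state compared with the state before treatment. The question asks how much effect is left now and does not say relative to what. A patient called long after the procedure can reasonably take it in two ways: how much better the knee is than before treatment, or how much of the benefit first obtained is still there. The two answers diverge where benefit has faded, which is what a late time point is meant to detect.

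At stake is the proportion of successes at the third time point. Patients who answer in the second sense could be counted as successes while falling short of the protocol's own definition. The anchored function item shows that the authors knew how to state the comparator.

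**Working it through.** The plan gives no figure to reproduce, and no sample size or error rate enters. The check compares the texts and then works out what the ambiguity could do.

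**Step 1: definition against instrument.**

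| Element | Reference point stated? | Where |
|---|---|---|
| Success definition, all time points | Yes, baseline | Section 4.1 |
| Success endpoint, third time point | Yes, baseline | Section 5.2 |
| Telephone item on perceived effect | No | Section 2.2 |
| Telephone item on function | Yes, before treatment | Section 2.2 |
| Week-6 GPE item | Wording not given | Sections 2.1 and 6 |

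**Step 2: the two readings.** Let E be the initial effect relative to baseline and r the share of it that remains at the call. The current effect relative to baseline is E × r.

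- Reading A (effect relative to before treatment): the answer is E × r, as the definition requires.
- Reading B (share of the benefit remaining): the answer is r.

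The documents give no values for E. Those below are assumptions for illustration.

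**Step 3: what an answer of 50% means under reading B.**

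- E = 50%: 0.50 × 0.50 = 25% relative to baseline
- E = 60%: 0.60 × 0.50 = 30%
- E = 80%: 0.80 × 0.50 = 40%
- E = 100%: 1.00 × 0.50 = 50%

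An answer above the threshold can also mislead. With E = 60% and an answer of 60%, the effect is 0.60 × 0.60 = 36%.

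**Step 4: share needed for true success.** The definition requires E × r ≥ 0.50, so r ≥ 0.50 / E. The recorded answer counts as success once r ≥ 0.50.

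| Assumed E | 0.50 / E | Answers wrongly counted as success |
|---|---|---|
| 60% | 0.833 | 50% to just under 83.3% |
| 70% | 0.714 | 50% to just under 71.4% |
| 80% | 0.625 | 50% to just under 62.5% |
| 90% | 0.556 | 50% to just under 55.6% |

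**Step 5: direction.** Since E is at most 1, E × r is at most r. Anyone who meets the definition (E × r ≥ 0.50) therefore also has r ≥ 0.50 and is counted. Reading B creates false successes and no false failures. The gap closes only at E = 100%.

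**Step 6: what cannot be computed.** The size of the bias in the reported proportion depends on how many patients adopt reading B and on the joint distribution of E and r. The documents give none of these, so no misclassification rate follows.

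**The case against.** The effect of a treatment is ordinarily understood relative to the state before it, and the word about persistence may mean no more than today. Section 2.2 says the call is held in Dutch, so patients do not hear the English wording. It also says the objectives are introduced and the required input explained before the questions. Section 2.1 intends the same variables as at week 6, and section 6 already schedules an NRS-based reduction of at least 50% at both time points.

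Much of this stands. It makes reading A plausible, perhaps usual, and one English word should not carry the case. It does not supply the missing comparator. The next item in the list also asks whether effect persists, so that framing is not confined to one word. If the Dutch script does contain the anchor, quoting it settles the matter.

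A reader might go further and infer three things that the documents do not support:

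- That the answers are on a different scale from the defined one. The item is ambiguous; a different scale is not demonstrated.
- That the third time point is not comparable with week 6. The week-6 wording is not given, so the two items could be identical. Section 7 also plans no comparison of GPE between the time points.
- That duration of effect inherits the problem. Section 5.2 defines duration by the same 50% threshold, but section 2.2 gives it a separate question that does not use the percentage item. That question states no threshold, which is a different matter.

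**Conclusion.** The point holds as a wording defect in the instrument for one secondary endpoint. The question as written does not ensure that third-time-point success is measured against baseline. If some patients report the share of benefit remaining, the success proportion is overstated and never understated. For each such patient, the true threshold is 0.83 to 0.56 of the initial benefit, for assumed initial effects of 60% to 90%, instead of 0.50.

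This rests on the assumed initial effects and on an unknown number of patients taking that reading, so it is a possible upward bias and not a shown misclassification. Whether the two GPE measurements match cannot be verified from the documents. The primary week-6 endpoint is unaffected. The change is still worth making, because a reported success proportion rests on this single item and the correction is nearly free.

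**What to change.** 1. Before calls start, anchor the item and keep it a global perceived effect on the same 0-100% scale. For example: *Compared with before the RF treatment, how much effect (0-100%) do you perceive now in this knee?* Use the same anchor in the Dutch script.
2. At both time points, cross-tabulate GPE of at least 50% against NRS reduction of at least 50%, which the section 6 schedule already lists. Baseline NRS is on file, so this check does not rely on the patient's choice of comparator. The two measures differ in content, so some disagreement is expected.
3. Report third-time-point success on both definitions, with the NRS version as a sensitivity analysis.
4. If calls are already done, report the cross-table and state the wording used as a limitation.

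Two remedies should be avoided. Restricting week-6 GPE to charts that record an explicit change from baseline could discard primary-endpoint data according to charting style. Replacing the item with a percentage change in pain that allows negative values would measure something other than global perceived effect and could create a mismatch with week 6.

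Cost: one reworded question, possibly an ethics notification if the script was approved, and one extra table.

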Main study endpoints: The main study outcome is the proportion of patients with a global perceived effect of at least 50% at 6 weeks post intervention. Secondary outcomes include reduction in pain intensity, measured by Numeric Rating Scale (NRS) at six weeks and at a third time point, global perceived effect at a third time point, subjective change in physical functioning, duration effect of the treatment, use of strong opioids, and adverse events.

PROTOCOL SYNOPSIS

Study Title	A retrospective single-center cohort study on patients with chronic knee pain treated with conventional radiofrequency of the genicular nerves.
Funder	ZOL Genk
Study Objectives	
Primary objective
 
• To evaluate treatment success of the conventional radiofrequency ablation at week 6 
Secondary objective
 
• Evaluation of treatment effect at a third time point at the end of the inclusion period• Subgroup analysis of treatment success based on indication to treatment• Evaluation of subjective functional improvement• Evaluation of change in analgesics• Estimation of the duration of effect of the treatment• Adverse events
Study Design	Retrospective single-center cohort study
Subject Population Key criteria for Inclusion and Exclusion:	
Inclusion Criteria
 
1. All patients with chronic knee pain who qualify for a conventional RF treatment of the genicular nerves 
Exclusion Criteria
 
1. Refusal to participate2. A negative diagnostic block with lidocaine 2% 1 ml of the three genicular nerves defined as less than 50% pain reduction3. Chronic widespread pain
Time	Patients treated with conventional RF treatment between 1 September 2017 and 30 June 2020.
Study endpoints	
1. Primary endpoint:
- Proportion of patients with treatment success at 6 weeks defined as GPE of $\geq 50\%$ compared to baseline.2. Secondary endpoints:
- Proportion of patients with treatment success at third time point defined as GPE of $\geq 50\%$ compared to baseline.- NRS reduction at week 6 and at the third time point- Subjective physical functioning at week 6 and at the third time point- Duration effect of the treatment defined as period with a GPE of $\geq 50\%$- Change in strong opioid use at week 6 and at the third time point- Safety: number/type of adverse events

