6. TIME SCHEDULE

Outcome / Time point	Baseline Consultation prior to inclusion	Diagnostic RF treatment	RF treatment	Consultation 6 weeks post treatment	Telephonic contact
Age	X				
Sex	X				
Duration of symptoms	X				
Previous knee surgery	X				
Referring physician	X				
Indication for treatment	X				
NRS	X			X	X
Strong opioid use	X			X	X
Chronic widespread pain	X				
NRS reduction $\geq 50\%$		X		X	X
Treating physician			X		
Subjective physical functioning score					X
GPE $\geq 50\%$				X	X
Adverse events				X	X
Informed consent					X

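### The only functioning item asks about improvement alone, so the functioning outcome cannot be reported as a change in both directions, and the score named in the schedule is not defined

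*Combined protocol and SAP*

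**What the plan says.** The outcome has several names in the combined protocol and SAP:

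- Abstract, main study endpoints: "subjective change in physical functioning".
- Section 4.2, secondary objectives (also in the abstract and synopsis): "Evaluation of subjective functional improvement".
- Section 5.2, secondary endpoints: "Subjective physical functioning at week 6 and at the third time point".
- Section 6, time schedule: "Subjective physical functioning score", marked at the telephone contact only.

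Section 2.1 says that the telephone contact will gather data "on subjective functional outcome", without naming an instrument. Section 2.2 gives the one question that does so: "Do you experience at the moment functional improvement in comparison with before the treatment". No response options, scale or coding follow it.

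**The concern.** A change can be for better or for worse, and a score has levels. The question asked has neither property. It asks whether there is improvement, and the natural replies are yes and no. A patient whose knee function is unchanged and one whose function has declined would both naturally answer no, and a slight gain counts the same as a large one.

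Decline is a realistic outcome here. The call may come up to 3 years after the procedure (section 2.1), and section 1 describes osteoarthritis as an active degenerative disease with loss of function among its symptoms. The study has one arm, so no comparison group is asked the same one-sided question. A reader given only a percentage improved would have no worsened share to set beside it.

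**Working it through.** The plan states no figure for this outcome, so there is nothing to reproduce. The check is whether any planned data could show worse function, followed by a short illustration.

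**1. Could change be derived from earlier measurements?** No. The baseline list in section 2.1 names the referring physician and otherwise reads "patient age, sex, NRS score, length of symptom duration, indication for the procedure, use of strong opioids, history of previous knee surgery". For week 6 it says: "Data collected at 6 weeks post-intervention will include: NRS, GPE, adverse events, and concomitant use of strong opioids". Neither list contains a functional measure, and section 6 marks functioning only at the telephone contact. The question in section 2.2 is the sole source. (That section 5.2 also promises functioning at week 6, with no item to supply it, is a separate matter.)

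**2. Is a score defined anywhere?** No. Section 6 is the only place that uses the word for this outcome. The Oxford Knee Score appears in the list of abbreviations but not in the objectives, endpoints, questionnaire, schedule or analysis. Section 7 offers means with standard deviations or medians with interquartile ranges, neither of which suits a yes/no answer.

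**3. Do the other telephone questions fill the gap?** Not for function.
- Perceived effect runs from 0 to 100%, so it has no negative range.
- The 0 to 10 pain rating can show worse pain, but not worse function.
- The adverse-event question is open, and a patient need not regard slow loss of function as an adverse event.

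**4. Is a balanced item feasible in this interview?** Yes. The tolerability question in the same list names both answers. The pain question also refers to the treated knee. The function question does not, although section 2.1 treats each knee as a separate observation.

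**5. Illustration, with assumed rates that are not from the documents.** Let b, s and w be the percentages of knees that are better, the same and worse, with b + s + w = 100. If answers are kept as yes or no, yes = b and no = s + w. The balance of improvement is b − w.

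| Assumed b / s / w | Yes | No | b − w |
|---|---|---|---|
| 40 / 60 / 0 | 40 | 60 + 0 = 60 | 40 − 0 = 40 points |
| 40 / 40 / 20 | 40 | 40 + 20 = 60 | 40 − 20 = 20 points |

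With b fixed, w can lie anywhere from 0 to 100 − b. For b = 40 the balance therefore ranges from +40 to 40 − 60 = −20 points. For b = 50 it ranges from +50 to 50 − 50 = 0 points. The yes share is the same throughout each range.

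**The case against.** The strongest reply is that the question measures what the study set out to measure. The objective in section 4.2, repeated in the abstract and synopsis, is functional improvement, and the item asks about exactly that. This stands. A reader might infer that the item fails the study's objective, but the documents do not support that. The mismatch is with the wording in the abstract's endpoint paragraph, section 5.2 and section 6.

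A reader might also infer that worsening will be recorded as no improvement. The plan does not say so. It gives no coding, the question is spoken, and a patient may answer that the knee is worse. What can be said is that no provision is made for such an answer.

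A third tempting reading is that functional harm from the procedure would go unseen. That goes too far. Adverse events are collected at week 6 and by telephone, have their own question and are a separate endpoint. Motor weakness is among the alarm symptoms about which patients are told. What remains uncaptured is mainly gradual decline and, without a control group, such decline could not be attributed to the treatment. It would still belong in a description of change.

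Two further points are fair. The calls are held in Dutch, so the printed English may not be the spoken wording, and no amount of bias towards yes can be shown. Any two-category outcome merges levels, the primary endpoint included, and the balance of improved minus worsened is not a planned endpoint. The illustration shows what is lost, not how much was lost here.

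**Conclusion.** The point holds as a measurement and labelling weakness in one of six secondary endpoints. One question, worded in the favourable direction only, is the sole source for an outcome that the plan elsewhere calls a change and a score. No score is defined, no response options are given, and unchanged and worse function are not separated. Change in both directions therefore cannot be reported from the planned data.

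The actual size cannot be computed, because the documents give no response rates. The illustrated differences rest on assumed rates and on answers being kept as yes or no. The primary endpoint is unaffected. Correcting this is a cheap improvement, not a condition for the study to be interpretable.

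**What to change.** Before the calls, replace the item in section 2.2 with a balanced one asked for each treated knee. For example: compared with before the treatment, is the function of this knee now much better, a little better, the same, a little worse or much worse? Report the full distribution, with the improved and worsened shares side by side. Replace the word score in section 6, and use one term for the outcome in the abstract and in sections 2.1, 4.2, 5.2 and 6.

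The cost is one reworded question and a slightly longer answer to record, with no added visits or staff. The new item would still rely on recall of pre-treatment function over up to 3 years. It does not supply a measured change, since there is no functional measure at baseline.

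If the calls are already done, name the outcome patient-reported functional improvement (yes/no) at the third time point, and state that deterioration was not measured.
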